## 5.7 Blinding

The study is an open-label study in terms of the investigational solution (2 mL radio-labelled saline) and the NMN pulse frequencies used where all participants will receive the same parameters but randomised at different study visit.

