### 2.3 Rational for current study

The proposed study aims to investigate the regional deposition in the nasal cavity of aerosols generated from the clinical NMN prototype using different pulse frequency modes. Information from this study will be used to aid in determining the optimal

deposition settings for future targeting of medication to the sinuses and within the nasal cavity.

Once beyond the nasal valve, the deposition pattern within the nasal cavity is vitally important. Deposition on middle meatus is of particular significance as this is the location of the ostiomeatal complex, a group of structures that receive drainage from the anterior and medial ethmoid cells, the frontal sinus and the maxillary sinus. Other important sites include the ostia of the sphenoid and posterior ethmoid sinuses, which are located superoposteriorly to the ostiomeatal complex on the sphenoethmoid recess and superior/supreme meatus, respectively. Improving the deposition to these regions is of clinical importance as it would translate into improved therapeutic effects in CRS, including patients that have undergone Functional Endoscopic Sinus Surgery (FESS).

To evaluate this, radio-labelled aerosols of a saline solution will be delivered using the clinical NMN prototype and sequential imaging will be performed using Single-photon emission computed tomography (SPECT) or positron emission tomography (PET) (depending on accessibility and availability of equipment in the hospital) and gamma scintigraphy imaging. Simultaneously, high resolution computed tomography (CT) scans of the nasal and sinus anatomy will be obtained from all participants and used as templates for overlaying subsequent deposition data to provide a detailed assessment of deposition characteristics.

Four different pulse frequency settings will be evaluated including: A) no pulse frequency (continuous delivery mode), B) a 10 Hz pulse frequency C) a 50 Hz pulse frequency and D) a 100 Hz pulse frequency based on preliminary *in vitro* studies and those investigated by other researchers [9].

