#### Interpretation and assumption of quantitative data

The quantitative assessment of nasal deposition, retention and clearance will be determined as a percentage of total nasal deposition (quantified using the first planar image immediately after inhalation of the radioaerosol) as a function of intensity within defined areas of the nasal cavity, left and right of the maxillary, frontal, ethmoidal and sphenoidal sinuses using standard protocol as briefly described below. Count rates in the selected region of interests will be analysed using the MATLAB Software or ImageJ Software packages (<http://rsb.info.nih.gov/ij/>). Count rates will be corrected for background activity and radioactive decay.

For analysis of the distribution of the radiolabelled saline into the different compartments, all serial images will be superimposed with regions of interest (ROI) of the nasal airways and sinuses defined as shown in Figures 6 and 7. The activity is obtained in these ROIs.

[figure not shown]

Figure 6. Regions of interest of the nasal cavity of the right and left maxillary and frontal sinuses (MR, FR, FL and ML). Image was taken from [9].

The primary endpoint of this study is the total area of distribution ( $\text{mm}^2$ ) of radiolabelled saline immediately after administration by the NMM ( $T_0$ ). This will be evaluated for each of subsites (surgically expanded ostia of the paranasal sinuses and oropharynx) and compared between treatments (A-D) which correspond to the different pulse frequencies tested. Between-treatment differences in total area of deposition of radiolabelled saline at each subsite will be compared by means of one-way analysis of variance (ANOVA) with application method as a factor.

Pairwise comparisons will be performed between each of the pulsed application methods and the continuous application (no pulse). Pairwise comparisons will be tested using a two-tailed p-value of  $<0.05$ .

Clearance will be calculated by the decrement in total radiolabelled saline between  $T_0$ ,  $T_{20}$  and  $T_{60}$ . Clearance will be evaluated for each subsite and compared between treatments (A-D). As with the primary efficacy endpoint, between-treatment differences in radiolabelled clearance will be tested by means of one-way analysis of variance (ANOVA) with application method as a factor. Pair-wise comparisons will be made between each of the pulsed application methods and the continuous application (no pulse).

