The retention of radiolabelled saline will be evaluated as the Area Under the Curve between  $T_0$  and  $T_{60}$  ( $\text{AUC}_{0-60}$ ) of the following assessments:

- the total area of deposition of radiolabelled saline
- the intensity of radiolabelled saline

The AUCs will be evaluated for each subsite and compared between treatments (A-D). Between-treatment differences in AUCs will be tested by means of one-way analysis of covariance (ANCOVA) with application method as a factor and the value at  $T_0$  as

covariate. Pair-wise comparisons will be made between each of the pulsed application methods and the continuous application (no pulse).

[figure not shown]

Figure 7. Example of superposition of anterior gamma camera images of radiolabelled aerosol after nasal delivery [9]. After deletion of the activity in the central nasal cavity, the aerosol penetration into the sinuses will be highlighted in B and D.

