## 5.6 Randomisation

Randomisation will occur once participant eligibility is confirmed.

Participants will be randomly assigned to one of the four possible study treatment frequencies in a fashion that ensures: that each individual receives each treatment.

The randomisation sequence will be generated by computer, prior to the study, by an independent statistician. The statistician will maintain a schedule of participant numbers and drug sequence allocation.

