### 8.2 8.2 Data collection

Data on individual participants, including demographic information, contact details and medical history, will be recorded in a paper file. The results of medical interviews, skin prick test and adverse events will also be recorded in the paper file at each study visit. Participants will have their unique identification number recorded on each sheet.

For lung function measurements, an electronic file will first be generated by the computer software for subsequent analysis. The file will be labelled with the participant's unique identification number. This data, once analysed, will be collated into a spreadsheet. The spreadsheet will identify participants only by their identification number.

Any imaging files taken off-site will be de-identified by removing identifying data from the images themselves, and by naming the electronic files by the participant's unique identification number only. However, the original files will remain stored on the RNSH Department of Nuclear Medicine servers in identifiable form, as per the requirements for clinical record keeping.

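### Pulse frequency is open with no provision for masked image reading, so region placement and the undefined edge of the primary area endpoint are exposed to reader bias that masked, pre-fixed image analysis would reduce

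*Protocol*

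**What the plan says.** Section 5.7 is the protocol's whole blinding rule: "The study is an open-label study in terms of the investigational solution (2 mL radio-labelled saline) and the NMN pulse frequencies used". It separates neither those who deliver the aerosol from those who process images, nor delivery from reading.

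The endpoint comes from images. Section 3.4 states: "The primary endpoint of this study is the total area of distribution", in mm², immediately after administration, evaluated by subsite and compared across the four settings. On the image step it says that "all serial images will be superimposed with regions of interest (ROI) of the nasal airways and sinuses", with the regions defined by reference to Figures 6 and 7. On software it says: "Count rates in the selected region of interests will be analysed using the MATLAB Software or ImageJ Software packages". The only stated corrections are for background and decay. The Figure 7 caption adds: "After deletion of the activity in the central nasal cavity, the aerosol penetration into the sinuses will be highlighted in B and D". (B and D there appear to be panels of that figure, not treatments B and D.)

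Some text limits discretion. Section 2.3 says the participants' CT scans are "used as templates for overlaying subsequent deposition data to provide a detailed assessment of deposition characteristics", and section 6.2.4 places the single CT at Visit 1.

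Three provisions bear on identity or allocation. Section 5.5 makes the participant number the identifier during analysis. Section 8.2 names imaging files taken off-site by the participant's "unique identification number only". Section 5.6 says of the independent statistician: "The statistician will maintain a schedule of participant numbers and drug sequence allocation".

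**The concern.** Participants and device operators can hardly be masked to the setting, and nothing here asks for that. Reading the images is a separate task done afterwards, and it can be masked even when delivery is open. The protocol does not take that step.

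Two features make it worth taking. The hypothesis in section 3.1 is directional: higher frequency is expected to improve sinus deposition. Section 2.3 intends the results to support registration of the device. If someone who knows the setting places or aligns a region, decides where labelled area ends, or removes central activity, those choices can lean towards the expected answer. With 10 or 11 participants, there is little to show afterwards whether a difference came from the device or from the reading.

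**Working it through.** The plan gives no figure to reproduce, so the check has three steps.

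**1. Does any provision mask the reader?**

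| Provision | What it does | Does it conceal frequency from the reader? |
|---|---|---|
| 5.7 | Makes frequency open | No; no exception for images |
| 5.5 | Participant number as analysis identifier | No; not a masked image code |
| 5.6 | Statistician holds the sequence schedule | No; the setting is open at each visit |
| 8.2 | De-identifies files taken off-site | No; protects privacy, and the originals stay identifiable on hospital servers |

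No provision requires masking, and none forbids it.

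**2. Where does judgement remain?**

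- Edge of the area: an area in mm² needs a rule for what counts as labelled. None is stated.
- Central activity: its deletion is mentioned without a rule, and it is not stated whether that step feeds the primary area.
- Regions: section 3.4 lists maxillary, frontal, ethmoidal and sphenoidal sinuses. The Figure 6 caption names only maxillary and frontal regions. The endpoint paragraph names surgically widened ostia and the oropharynx, although section 5.3.2 excludes a history of upper-airway surgery.
- Alignment: images from Visits 2 to 4 must be matched to a CT taken at Visit 1.

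The CT template and Figures 6 and 7 constrain the regions. They do not settle the area edge or the alignment.

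**3. What would reader bias do to the contrast?**

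Write the recorded area for participant i at setting j as

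Y_ij = A_ij + r_i + d_j,

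where A is the true area, r_i a reader preference common to that participant's four image sets, and d_j a preference tied to the setting. For pulsed setting j against continuous (0):

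Y_ij − Y_i0 = (A_ij − A_i0) + (d_j − d_0).

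The common term r_i cancels. A common proportional preference would rescale a true difference but would not create one. The term d_j − d_0 stays in full. Randomising the order does not average it out, because it follows the setting and not the visit.

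For sensitivity only, assume no true difference and a constant differential bias of b standard deviations of the within-participant difference. Take a two-sided paired t-test at 0.05 (section 3.4 sets two-tailed 0.05 for pairwise comparisons), with n = 10 (section 5.1) or n = 11 completers (section 4.3). The rejection rate comes from the noncentral t distribution with n − 1 degrees of freedom and noncentrality b√n; for example, 0.5 × √10 = 1.58.

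| Assumed b | n = 10 | n = 11 |
|---|---|---|
| 0 | 0.050 | 0.050 |
| 0.25 | 0.109 | 0.117 |
| 0.50 | 0.293 | 0.323 |
| 0.75 | 0.562 | 0.612 |
| 1.00 | 0.803 | 0.848 |

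Every non-zero b is an assumption. The paired test is also a simplification: the protocol names a one-way ANOVA, for which the rates would differ. The table shows how sensitive a small study is to differential bias. It is not evidence that such bias will occur.

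**The case against.** The strongest reply is that this is silence, not error. Section 5.7 describes how the study is run and does not say who reads the images or what they know. Open delivery is compatible with masked reading, and an image-analysis manual or SAP could require it. The study is described as exploratory and as a pilot. The CT template already comes close to fixing regions once per participant, and section 3.4 refers to a standard protocol for quantification. Figures 6 and 7 are not visible in the text available here, so the remaining discretion cannot be measured.

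Much of this stands. It limits the point to what the plan permits, not what will happen. It does not dispose of it: the protocol states a blinding rule, that rule has no exception for image work, and masking has to be in place before images are read.

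Three stronger readings are tempting and unsupported:

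- A reader might infer that analysts set activity thresholds. The protocol mentions no threshold and does not say who sets one. What can be said is that the area edge is undefined.
- A reader might size the bias by moving the outline of a region by a millimetre or so and computing the change in its area. The documents give no region size or shift. The endpoint is the area of labelled saline, so widening an outline adds area only where labelled saline lies in the added rim. A shift made alike at all four settings would not appear as a frequency effect.
- A reader might infer that masking would remove reader bias. The deposition pattern itself may hint at the setting, and delivery and participant technique stay unmasked.

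**Conclusion.** The concern holds in limited form. As written, the plan permits image analysis by someone who knows the pulse frequency, for a primary endpoint whose edge is undefined, under a directional hypothesis and with registration in view. Any preference that differs by frequency enters the within-participant contrast undiminished.

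Its size is unknown: the documents give no figure for reader bias or for the variability of the area, so the gain from masking cannot be estimated from them. The conclusion rests on two inferences: that some human choice remains in region alignment and area definition, and that no document outside the protocol already masks the reading. Because the remedy is cheap and leaves administration unchanged, it should be adopted before any images are read, even in an exploratory study.

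**What to change.** Add one paragraph to section 5.7, cross-referenced from section 3.4:

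1. Administration stays open; image analysis is masked to pulse frequency.
2. The independent statistician who holds the allocation schedule recodes copies of each participant's four image sets with random labels that carry no visit number, date or frequency. Readers work only from these copies.
3. Regions are defined once per participant on the Visit 1 CT, from a single stated list of subsites, and applied to all four visits. Alignment to the CT is done on the recoded images.
4. One area cut-off, and one rule for removing central nasal activity if that step is used, are fixed in advance and applied identically to every image set.
5. The frequency code is released only after the region and area files are locked.

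The cost is that paragraph, a few hours of file recoding and some co-registration bookkeeping. No additional reader, scan or participant is needed.

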## 5.8 Incidental findings

Although unlikely, making incidental findings on medical imaging and during screening can occur and may warrant further investigation. For example, lesions may be detected on the CT scan that may represent early, asymptomatic cancers. In the event of such a finding, the study investigators will inform both the participant and, with permission, their primary care physician. An assessment as to the significance of the finding will be given to the participant/physician. If immediate investigation is thought to be necessary, this recommendation will be made by the study investigators and the participant removed from the study. If immediate investigation of the lesion is not considered to be necessary, the participant will be reminded that they may withdraw from the study at any time in order to pursue further investigation.

## 5.9 Participant withdrawal

In accordance with the Declaration of Helsinki, the Investigator must explain to the participant that they have the right to withdraw from the study at any time, and that this will in no way prejudice their future treatment.

Participants will be encouraged to complete the study; however, they may voluntarily withdraw at any time. The Investigator will provide a written report on the appropriate CRF page describing the reason for discontinuation and included in a final study report to the HREC.

A participant may be removed from the study for the following medical or alternative reasons:

- Adverse event
- If a participant suffers an adverse event that, in the judgement of the Investigator or the Sponsor, presents an unacceptable consequence or risk to the participant, the participant may be discontinued from further participation in the study.
- Intercurrent illness
- A participant may also be discontinued from the study if, in the judgement of the Investigator, he or she develops an intercurrent illness or complication that is not consistent with the protocol requirements or that, in any way, justifies his or her withdrawal from the study.
- Failure of participant to comply fully with protocol required safety and/or efficacy assessments or general protocol non-compliance (in the opinion of the investigator at his/her discretion)

If a participant withdraws:

- prior to treatment but after CT scans, the CT scans data of the participant can be utilised for developing an anatomical model and another participant enrolled.
- After initial treatment (visit 1) but before final treatment (visit 4) then the participant's data will be placed in a subsidiary file and a replacement participant enrolled.

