#### **4.3 Number of participants**

Employing a cross-over design enables each participant to act as its own control, and reduces the overall number of patients needed to assess aerosol deposition.

For this investigational study, participants who meet all the eligibility criteria will be enrolled and randomised into the study until 11 participants who complete the study are met.

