## **5.0 Study population**

## 5.1 Sample size calculation

A previous study that investigated the temporo-spatial deposition of saline delivered by a squeeze bottle, nasal saline spray and nasal gel enrolled 5 healthy subjects (**Bleier et al. 2011**). Similarly, a PARI VibrENT nebulizer system that evaluated the pulsating aerosol (fixed frequency of 25 Hz) to the sinuses was conducted with five healthy volunteers (**Moller et al 2010**). Taking into account that four different pulse frequencies are evaluated a sample size of minimum 10 subjects will be sufficient for this pilot study.

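### Protocol sections 5.9 and 4.3 together appear to confine the imaging analyses to the 11 completers, setting aside usable visits of treated participants who leave early

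*Protocol*

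**What the plan says.** Section 5.9 of the protocol separates two kinds of withdrawal. If someone leaves after the CT scan but before any treatment, the scan may still be used for the anatomical model. If someone leaves after visit 1 but before the visit 4 treatment, the "data will be placed in a subsidiary file and a replacement participant enrolled". No use is given for that file.

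Section 4.3 sets the enrolment target: eligible people are "enrolled and randomised into the study until 11 participants who complete the study are met". The same section gives the reason for the design: "Employing a cross-over design enables each participant to act as its own control".

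Section 3.4 (Interpretation and assumption of quantitative data) compares the settings by "one-way analysis of variance (ANOVA) with application method as a factor", first for area of distribution and then for clearance. Retention is analysed by a one-way ANCOVA with the value at T0 as covariate. The section defines no analysis set for these endpoints and does not mention the subsidiary file.

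Two other places bear on the point. Section 3.5 collects adverse events for everyone randomised and reports them in a safety population. Section 5.7 makes the study open-label for pulse frequency.

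**The concern.** A participant can be treated and imaged at up to three visits and then drop out of the main data set because a fourth visit did not take place. The removal reasons in section 5.9 include an adverse event and non-compliance as judged by the investigator. Either could follow the setting just used; section 7.1.1 itself anticipates nose irritation or stinging from the device. Because the setting is known to all, a discretionary removal is made with that knowledge, and under section 5.9 it also takes the participant's earlier images out of the comparison.

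Two things are at stake. One is possible selection in a comparison meant to identify the best frequency (section 3.2). The other is the waste of images that carry information on the contrasts and were obtained at a radiation cost: from Table 2, a participant with three visits has received 1.9 + 3 × 0.24 = 2.62 mSv.

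**Working it through.** **Reading the sections together.** The pre-treatment case in section 5.9 says what the data may be used for. The post-treatment case says only that they are filed separately and the person replaced. Section 4.3 counts completers, and section 3.4 has no step that uses the separate file. Nothing in the protocol contradicts exclusion, but nothing states it outright.

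**The plan's own figure.** Section 5.1 says "a sample size of minimum 10 subjects will be sufficient for this pilot study", by reference to two earlier studies of five people. It gives no effect size, SD, power or withdrawal rate, so there is no power figure to reproduce. For context, assume 80% power and two-sided 0.05. A paired comparison then detects about 1.00 SD of the paired difference with 10 participants and 0.94 SD with 11. Replacement protects that level of precision.

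**What the set-aside visits are worth.** Inputs: 4 settings and 11 completers (sections 4.2 and 4.3). Assumptions, since the protocol gives no figures: m = 1 to 3 withdrawers, each with k imaged visits, and missing settings spread evenly. The model has a fixed participant term and a treatment term; period is left out for simplicity.

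After the participant's own level is estimated, k visits leave k − 1 within-participant degrees of freedom, against 3 for a completer. With missing settings spread evenly:

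- worth of a withdrawer = (k − 1)/3 of a completer: 0.67, 0.33 and 0 for k = 3, 2 and 1;
- variance of a difference between two settings = 2σ² / (11 + m(k − 1)/3);
- ratio to completers-only = 11 / (11 + m(k − 1)/3).

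| Withdrawers m | k = 3 | k = 2 | k = 1 |
|---|---|---|---|
| 1 | 11/11.67 = 0.943 (−5.7%) | 11/11.33 = 0.971 (−2.9%) | 1 (0%) |
| 2 | 11/12.33 = 0.892 (−10.8%) | 11/11.67 = 0.943 (−5.7%) | 1 (0%) |
| 3 | 11/13 = 0.846 (−15.4%) | 11/12 = 0.917 (−8.3%) | 1 (0%) |

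In standard-error terms even the largest entry is small: √0.846 = 0.920, an 8% reduction. With a random participant effect and an assumed within-participant correlation of 0.3 to 0.7, the worth rises slightly, to 0.68–0.70, 0.36–0.42 and 0.08–0.18 of a completer for three, two and one visits.

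As a count of images, two withdrawers with three visits each would set aside 6 of 11 × 4 + 6 = 50 image sets, or 12%.

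**Why the stated model matters.** These figures need a participant term, which the one-way ANOVA lacks. Among completers every setting is averaged over the same 11 people, so participant levels cancel from the mean differences even without that term. Once incomplete participants are added they no longer cancel, and differences between people would enter the comparison of settings. The data rule and the model therefore have to change together.

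**The case against.** The strongest reply is that section 5.9 is a rule about filing and enrolment, not an analysis rule, and that analysis sets are commonly left to a SAP. A reader might infer that the protocol expressly discards these data. It does not: exclusion is inferred, and the images are kept. What remains is that the protocol states a rule whose natural reading is exclusion. A SAP with a wider set would have to say how it fits with that rule.

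A reader might also infer that the frequency comparison is biased. The documents do not support that. Every completer receives all four settings, so restricting to completers creates no imbalance between them. Bias would need withdrawal to be linked to a participant's own deposition differences between settings, not merely to tolerability. The volunteers are healthy and only mild discomfort is expected, so such a link is possible but not shown.

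Third, replacement preserves the 11 completers, above the stated minimum of 10. The partial visits would be a gain beyond the plan, not a loss from it. That is correct. It is also correct that a one-visit withdrawer gives no within-participant contrast.

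Finally, some images from people removed for non-compliance may be unsuitable; section 5.3.2, for instance, requires a negative cotinine test at each visit. This is why the remedy refers to valid visits. Reasons for discontinuation are also recorded and reported to the ethics committee, so a pattern by setting could be seen, although that does not decide how the data are analysed.

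**Conclusion.** The point holds in a limited form. Sections 5.9 and 4.3 appear to restrict the deposition, clearance and retention analyses to completers. Selection on completion is a possibility that the protocol leaves open, with size and direction unknown.

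The gain from using the partial visits is modest: about 6–15% in variance for one to three withdrawers with three visits each, 3–8% with two visits each, and none with one visit each. It rests on assumed withdrawal numbers, evenly spread missing settings and a model with a participant term. In an exploratory pilot this is not a fatal flaw. It should still be corrected, because the images already exist and using them needs no further procedures.

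**What to change.** Keep replacement as an enrolment rule and make two linked amendments.

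1. In section 5.9, state that all valid imaged visits of treated participants enter the primary analysis, whether or not all four visits were completed. Define a valid visit in advance, without reference to the deposition result.
2. In section 3.4, replace the one-way ANOVA with a model containing participant (for example as a random effect), period and treatment, and carry the same structure into the clearance and retention analyses. State that its use of incomplete participants is valid if missingness depends on observed data.

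Report the completers-only analysis as a sensitivity analysis.

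The cost is an amendment to the wording and a real change to the stated primary model, plus a slightly unbalanced data set. No additional imaging or radiation exposure is involved.
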